### **3.4. Baseline Variables**

#### **3.4.1. Demographic, Medical History, and Baseline Characteristic Variables**

Demographic variables collected at Visit 1 include sex, race, ethnicity, and date of birth. Race collected includes:

- Black or African American
- American Indian or Alaska Native
- Asian
- Native Hawaiian or other Pacific Islander
- White
- Not reported

Ethnicity collected includes:

- Hispanic or Latino
- Non-Hispanic/non-Latino
- Not reported

For countries where full date of birth is collected, age at the time of first vaccination and age at randomization will be derived based on birthday. For example, if the first vaccination date is 1 day before the participant's thirteenth birthday, the participant is 12 years old.

Medical history will be assessed at Visit 1 and categorized according to the current version (at the time of reporting) of MedDRA.

Physical examination will be assessed prior to vaccination at Visit 1 (Groups 1 and 2) and each body system examined will be recorded in the CRF as normal, abnormal, or not done. Additional physical examination prior to Vaccination 2 (Groups 1 and 2) and Vaccination 3 (Group 2 only) will also be recorded on the CRF, but with fewer body systems.

#### **3.4.2. Previous Vaccinations**

For participants who have ever received a PRP-OMP vaccine, the name of the vaccine and date of administration will be recorded on the CRF.

### **3.5. Safety Endpoints**

#### **3.5.1. Adverse Events**

For all participants, information about AEs will be collected for events occurring within approximately 1 month after each vaccination, and information about SAEs, including hospitalizations, MAEs, and NDCMCs, will be collected for events occurring approximately 6 months after Vaccinations 1 and 2, and within approximately 1 month after Vaccination 3.

Information about AEs and SAEs, including hospitalizations and MAEs, will be collected for events occurring within 48 hours after each antibody persistence blood draw.

All events collected on the CRF will be categorized according to the current version (at the time of reporting) of MedDRA.

Details for the collection of AE and SAE information for participants in each vaccine group are described below.

### **Group 1 (0- and 12-Month Schedule)**

The time period for actively eliciting and collecting AEs and SAEs (“active collection period”) for each participant begins from the time the participant’s parent(s)/legal guardian provides informed consent, which is obtained before the participant’s participation in the study (ie, before undergoing any study-related procedure and/or receiving study intervention), through and including Visit 2 (1 month after the first dose of MenABCWY), and from Visit 4 (second dose of MenABCWY) to Visit 5 (1 month after the second dose of MenABCWY).

At Visit 3 (safety telephone contact, 6 months after the first dose of MenABCWY), the participant’s parent(s)/legal guardian will be contacted by telephone to inquire about SAEs, MAEs, and NDCMCs since Visit 2.

At Visit 6 (12-month antibody persistence visit), information about SAEs, MAEs, and NDCMCs will be collected for events within 6 months after Visit 4 (second dose of MenABCWY).

During the antibody persistence phase (Visits 6 and 7), information about AEs and SAEs, including hospitalizations, MAEs, and NDCMCs, will be collected for events occurring within 48 hours after each antibody persistence blood draw.

AE collection for Group 1 (0- and 12-month schedule) is summarized in [Table 3](#).

### **Group 2 (0- and 36-Month Schedule)**

The time period for actively eliciting and collecting AEs and SAEs (“active collection period”) for each participant begins from the time the participant’s parent(s)/legal guardian provides informed consent, which is obtained before the participant’s participation in the study (ie, before undergoing any study-related procedure and/or receiving study intervention), through and including Visit 2 (1 month after the first dose of MenABCWY), and from Visit 4 (placebo dose) to Visit 5 (1 month after the placebo dose) and from Visit 9 (second dose of MenABCWY) to Visit 10 (1 month after the second dose of MenABCWY).

At Visit 3 (safety telephone contact, 6 months after the first dose of MenABCWY), the participant’s parent(s)/legal guardian will be contacted by telephone to inquire about SAEs, MAEs, and NDCMCs since Visit 2.

At Visit 8 (safety telephone contact, 12 months after the placebo dose), the participant's parent(s)/legal guardian will be contacted by telephone to inquire about SAEs, MAEs, and NDCMCs within 6 months after Visit 4 (placebo dose).

AE collection for Group 2 (0- and 36-month schedule) is summarized in [Table 4](#).

Follow-up by the investigator continues throughout and after the active collection period and until the AE or SAE or its sequelae resolve or stabilize at a level acceptable to the investigator and Pfizer concurs with that assessment.

For participants who are screen failures, the active collection period ends when screen failure status is determined.

If the participant withdraws from the study and also withdraws consent for the collection of future information, the active collection period ends when consent is withdrawn.

**Table 3. Summary of Adverse Event Collection for Group 1 (0- and 12-Month Schedule)**

	Visit 1	Visit 2	Visit 3	Visit 4	Visit 5	Visit 6	Visit 7 a
Visit Description	Vaccination 1	1-Month Post-Vaccination 1 Blood Draw	Safety Telephone Contact 1	Vaccination 2	1-Month Post-Vaccination 2 Blood Draw	12-Month Antibody Persistence Visit	24-Month Antibody Persistence Visit
Approximate Month	0	1	6	12	13	24	36
Nonserious AEs						Within 48 hours after blood draw	Within 48 hours after blood draw
SAEs						b,c	Within 48 hours after blood draw
MAEs						b,c	Within 48 hours after blood draw
NDCMCs						b	

Abbreviations: MAE = medically attended adverse event; NDCMC = newly diagnosed chronic medical condition.

Note: The arrows represent the time periods for safety data collection.

a. Visits 8, 9, and 10 will not be conducted for Group 1 participants.

b. Events occurring within 6 months after Vaccination 2.

c. Events occurring within 48 hours after the Visit 6 blood draw.

**Table 4. Summary of Adverse Event Collection for Group 2 (0- and 36-Month Schedule)**

	Visit 1	Visit 2	Visit 3	Visit 4	Visit 5 a	Visit 8	Visit 9	Visit 10
Visit Description	Vaccination 1	1-Month Post-Vaccination 1 Blood Draw	Safety Telephone Contact 1	Vaccination 2	1-Month Post-Vaccination 2 Blood Draw	Safety Telephone Contact 2	Vaccination 3	1-Month Post-Vaccination 3 Blood Draw
Approximate Month	0	1	6	12	13	24	36	37
Nonserious AEs	↔			↔			↔	
SAEs	↔			↔ b		↔		
MAEs	↔			↔ b		↔		
NDCMCs	↔			↔ b		↔		

Abbreviations: MAE = medically attended adverse event; NDCMC = newly diagnosed chronic medical condition.

Note: The arrows represent the time periods for safety data collection.

a. Visits 6 and 7 will not be conducted for participants in Group 2.

b. Events occurring within 6 months after Vaccination 2.

### 3.5.1.1. Analysis Intervals

There will be 11 analysis intervals for the AE data collected via CRF (Table 5). The analysis populations used for these intervals are described in detail in Section 4.

For Vaccination 1 (Visit 1), MenABCWY will be administered to participants in both Groups 1 and 2. For Vaccination 2 (Visit 4), MenABCWY will be administered to Group 1 participants; saline will be administered to Group 2 participants. For Vaccination 3 (Visit 9), MenABCWY will be administered to Group 2 participants.

**Table 5. Analysis Intervals for AEs, SAEs, MAEs, NDCMCs, and Days Missing School or Work Because of AEs**

Interval #	Group	Analysis Interval	Analysis Population	Interval Start Date (Inclusive)	Interval Stop Date (Inclusive)	Safety Data
1	Groups 1, 2	Within 30 days after Vaccination 1	Vax 1 safety	Vax 1 date (Visit 1 for Groups 1, 2)	Vax 1 date (Visit 1 for Groups 1, 2) + 30 days	AEs, SAEs, MAEs, NDCMCs
2	Groups 1, 2	Within 30 days after Vaccination 2	Vax 2 safety	Vax 2 date (Visit 4 for Groups 1, 2)	Vax 2 date (Visit 4 for Groups 1, 2) + 30 days	AEs, SAEs, MAEs, NDCMCs
3	Group 2	Within 30 days after Vaccination 3	Vax 3 safety	Vax 3 date (Visit 9 for Group 2)	Vax 3 date (Visit 9 for Groups 1, 2) + 30 days	AEs, SAEs, MAEs, NDCMCs
4	Groups 1, 2	Within 30 days after any MenABCWY vaccination	Safety	Vax 1 date (for Groups 1, 2) or Vax 2 date (for Group 1) or Vax 3 date (for Group 2)	Vax 1 date (Groups 1, 2) + 30 days or Vax 2 date (Group 1) + 30 days or Vax 3 date (Group 2) + 30 days	AEs, SAEs, MAEs, NDCMCs
5	Groups 1, 2	Vaccination 1 vaccination phase	Vax 1 safety	Visit 1 date	Visit 2 date (or end of vaccination day)	AEs, SAEs, MAEs, NDCMCs
6	Groups 1, 2	Vaccination 2 vaccination phase	Vax 2 safety	Visit 4 date	Visit 5 date (or end of vaccination day)	AEs, SAEs, MAEs, NDCMCs
7	Group 2	Vaccination 3 vaccination phase	Vax 3 safety	Visit 9 date	Visit 10 date (or end of vaccination day)	AEs, SAEs, MAEs, NDCMCs, days missing school or work because of AEs
8	Groups 1, 2	During follow-up phase 1	Follow-up safety 1	Visit 2 date + 1, or end of vaccination date + 1 for early withdrawal participants	6 Months after Vax 1 date (Visit 3)	SAEs, MAEs, NDCMCs
9	Groups 1, 2	During follow-up phase 2	Follow-up safety 2	Visit 5 date + 1, or end of vaccination date + 1 for early withdrawal participants	6 Months after Vax 2 date	SAEs, MAEs, NDCMCs

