2.3. Benefit/Risk Assessment

Common AEs noted after vaccination with Trumenba (licensed in the US, EU, and other countries) and Nimenrix (licensed in the EU and other non-US countries) are primarily related to reactogenicity, including local reactions (pain, swelling, redness around the injection site) and systemic events (headache, fatigue, myalgias, arthralgias, nausea/vomiting, diarrhea, chills, fever). As noted above, the MenABCWY profile from the Phase 2 portion of Study B1971057 is consistent with these 2 licensed products.

As with any vaccine, an allergic reaction may occur. Symptoms of an allergic reaction can include swelling of the lips, mouth, and throat, which may cause difficulty in swallowing or breathing; skin rash; swelling of the hands, feet, and ankles; dizziness; and fainting. A severe allergic shock (anaphylactic shock) may occur. There may also be additional risks related to the vaccines administered in the study that are unknown at this time.

Risks that may be associated with study procedures include risk from blood sampling, such as feeling faint, dizziness, fainting, pain, swelling, bruising, and infection in the vicinity of the vein from where blood is taken.

Safety assessments described in this protocol and ongoing safety data reviews by the investigator, and the sponsor's global medical monitor, the internal safety data review subcommittee, the internal risk management committee, and the E-DMC will serve to monitor and mitigate these risks.

In Phase 2 Study B1971057, MenABCWY provided a high degree of immunologic protection against IMD caused by *N meningitidis* serogroups A, B, C, W, and Y based on the proportions of participants achieving hSBA titers \geq LLOQ for each serogroup (\geq 1:8 for serogroups A, C, W, and Y and \geq 1:8 or \geq 1:16 for serogroup B, depending on the test strain), which are higher than the accepted surrogate marker for protective immunity (hSBA titer \geq 1:4). Additionally, MenABCWY was statistically noninferior to Trumenba for the B component and MenACWY-CRM for the ACWY components in both ACWY-naïve participants and ACWY-experienced participants. This Phase 2b study is one of several studies comprising the MenABCWY development program, which if successful, could provide a broadly protective, safe, comprehensive, and first-in-class meningococcal vaccine that could contribute significantly to a simplified vaccination program for the prevention of IMD.

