8.2. Safety Assessments

Planned time points for all safety assessments are provided in the [SoA](#). Unscheduled clinical laboratory measurements may be obtained at any time during the study to assess any perceived safety issues.

Any participant who receives at least 1 dose of study intervention will be included in the evaluation for safety. The following safety parameters will be assessed as described in [Section 8.11](#) and in the [SoA](#):

- Physical examination;
- AEs and SAEs.

A medical history will be obtained, and a physical examination will be performed on all participants at Visit 1 to establish a baseline. When taking the medical history and performing the physical examination, particular care must be taken to note any neuroinflammatory and autoimmune conditions, such as transverse myelitis, uveitis, optic neuritis, and multiple sclerosis. Significant medical history and observations from the physical examination will be documented on the CRF. In addition, a urine pregnancy test will be performed on all female participants.

Immediate AEs, defined as AEs occurring within the first 30 minutes after study intervention administration, will be assessed and documented on the AE CRF. The time of onset will be recorded for any AEs that occur on the same day as study intervention administration.

MAEs and NDCMCs will also be assessed throughout the study and documented on the appropriate AE CRF. An MAE is defined as a nonserious AE that results in an evaluation at a medical facility. An NDCMC is defined as a disease or medical condition, not previously identified, that is expected to be persistent or otherwise long-lasting in its effects.

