8.11. Study Procedures

8.11.1. Group 1 (0- and 12-Month Schedule)

8.11.1.1. Visit 1 (Day 1), Vaccination 1

In the case of temporary delay of vaccination, procedures and assessments below will be redone or reconfirmed, as applicable, on the day of vaccination.

- Obtain written informed consent, and assent if appropriate, before performing study-specific procedures. The date of informed consent will be recorded on the CRF.
- Record the participant's demographic information (including date of birth, sex, race, and ethnicity). The full date of birth will be collected to critically evaluate the immune response and safety profile by age.
- Record the presence of chronic conditions and/or medical history of significance, including relevant surgical procedures and cardiac medical history.
- Record previous PRP-OMP vaccinations as described in [Section 6.5.3](#).
- Perform a physical examination evaluating any clinically significant abnormalities within the following body systems: general appearance; skin; head, eyes, ears, nose, throat; heart; lungs; abdomen; extremities; neurological; musculoskeletal; and lymph nodes; including worsening of medical history conditions. Results must be recorded on source documents and the CRF. Findings from a physical examination conducted as part of standard routine care and before informed consent may be used for purposes of the study only if the examination was performed no more than 2 days before vaccination. A brief examination must be performed on the day of vaccination to document that no change in health has occurred in the interim.
- On the day of vaccination, perform a urine pregnancy test on female participants. A negative pregnancy test result is required before the participant may receive the study intervention.
- On the day of vaccination, prior to administration of study intervention, measure and record the participant's oral temperature.
- Ensure that all of the inclusion criteria, none of the exclusion criteria, and none of the temporary delay criteria are met.

- If a participant is eligible for the study, assign a randomization number and an investigational product container number via the IRT, or an equivalent system.
- On the day of vaccination, prior to administration of study intervention, collect a blood sample (approximately 25 mL). Collect the blood sample only if the participant is eligible for vaccination on the same day.

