**Table 5. Analysis Intervals for AEs, SAEs, MAEs, NDCMCs, and Days Missing School or Work Because of AEs**

Interval #	Group	Analysis Interval	Analysis Population	Interval Start Date (Inclusive)	Interval Stop Date (Inclusive)	Safety Data
10	Groups 1, 2	6 Months after Vaccination 1	Vax 1 safety	Vax 1 date (Groups 1, 2)	6 Months after Vax 1 date	SAEs, MAEs, NDCMCs, days missing school or work because of AEs
11	Groups 1, 2	6 Months after Vaccination 2	Vax 2 safety	Vax 2 date (Groups 1, 2)	6 Months after Vax 2 date	SAEs, MAEs, NDCMCs, days missing school or work because of AEs

Abbreviations: MAE = medically attended adverse event; NDCMC = newly diagnosed chronic medical condition; Vax = vaccination.

Note: 183 Days will be used as the duration for programmatic determination of 6 months for Interval 11.

Three analysis intervals will be applied to immediate AEs (Table 6).

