**Table 6. Analysis Intervals for Immediate AEs**

Interval #	Group	Analysis Interval	Analysis Population	Interval Start Date/Time (Inclusive)	Interval Stop Date/Time (Inclusive)
1	Groups 1, 2	Vaccination 1	Vax 1 safety	Vax 1 time	Vax 1 time + 30 minutes
2	Groups 1, 2	Vaccination 2	Vax 2 safety	Vax 2 time	Vax 2 time + 30 minutes
3	Group 2	Vaccination 3	Vax 3 safety	Vax 3 time	Vax 3 time + 30 minutes

Abbreviation: Vax = vaccination.

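### SAP Table 5 starts its vaccination intervals at a calendar date, so AEs that begin before the injection on a vaccination day are counted as post-vaccination events

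*SAP*

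**What the plan says.** - **Interval boundaries.** In SAP 3.5.1.1, Table 5, the start column is headed "Interval Start Date (Inclusive". Interval 1 opens at "Vax 1 date (Visit 1 for Groups 1, 2", Interval 2 at "Vax 2 date (Visit 4 for Groups 1, 2" and Interval 10 at "Vax 1 date (Groups 1, 2". Intervals 3, 4 and 11 also open at vaccination dates. Intervals 5, 6 and 7 open at the dates of Visits 1, 4 and 9. None uses a clock time.
- **AE collection.** Protocol 8.3.1 and SAP 3.5.1 start active collection at informed consent, ahead of any procedure or dose.
- **Order of events at Visit 1.** Protocol 8.11.1.1 says "On the day of vaccination, prior to administration of study intervention, collect a blood sample (approximately 25 mL". Protocol 8.11.2.1 has the same step for Group 2.
- **Known procedure risks.** Protocol 2.3: "Risks that may be associated with study procedures include risk from blood sampling, such as feeling faint, dizziness, fainting, pain, swelling, bruising".
- **Times on record.** Protocol 8.2: "The time of onset will be recorded for any AEs that occur on the same day as study intervention administration". The visit procedures also put the injection time on the CRF.
- **Immediate AEs.** SAP Table 6 does use clock time. For Vaccination 1 its window opens at the vaccination time and closes at "Vax 1 time + 30 minutes".

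**The concern.** The Table 5 labels and the primary safety estimand speak of events after vaccination, but the programmed boundary takes in the whole vaccination day. A participant who faints during the pre-dose draw and is then injected falls outside the Table 6 window yet inside the 30-day count after Vaccination 1. The two tables treat the same event differently.

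Nothing else in the SAP removes such an event. The missing-date rule in SAP 5.3.1 does not apply, because the date is known. The related-event summary in SAP 6.6.1.1 is a separate table and leaves the any-AE percentage unchanged.

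The percentage with at least one AE in the 30 days after each vaccination, and in each vaccination phase, is a primary safety summary (Protocol 3, SAP 2.1.4). Events caused by study procedures could therefore be reported there as events that followed the vaccine.

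**Working it through.** No figure in the plan depends on the interval rule, so there is no disputed number to reproduce. The check is a reading of the rule, followed by a sizing under stated assumptions.

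**Step 1. Which intervals follow the date rule.**

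| Injection visit | Intervals starting on that date | Pre-injection AE sources on that day |
|---|---|---|
| Visit 1 (both groups) | 1, 4, 5, 10 | Consent period, physical examination, 25 mL draw |
| Visit 4 (both groups) | 2, 6, 11; also 4 for Group 1 | AE checklist, brief physical examination; no draw |
| Visit 9 (Group 2) | 3, 7; also 4 | AE checklist, brief physical examination; no draw |

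The rule is the same at all three visits. The consent period and the pre-dose draw are specific to Visit 1 (SAP 2.2 places the only pre-vaccination draw before Vaccination 1). Interval 4 pools all MenABCWY doses. Intervals 10 and 11 cover SAEs, MAEs, NDCMCs and missed days, so only those outcomes can be affected there.

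**Step 2. When a percentage changes.** The summary counts participants with at least one event. A pre-injection AE adds a participant only if that person has no other AE in the interval. Let q be the proportion with a pre-injection AE on the vaccination day, and p the proportion with at least one true post-injection AE, taken as independent. Then

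addition to the percentage = q × (1 − p).

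**Step 3. Inputs.**
- n = 150 per group (Protocol 9.2).
- q is not given anywhere; 0%, 1%, 2% and 5% are assumed.
- p is assumed to run from 10% to 39.2%. The upper end is the any-AE percentage for MenABCWY recipients in Study B1971057 (Protocol 2.2.2.3). It covers a longer window, from the first dose to 1 month after the second, so it serves only as the top of the range.

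**Step 4. Results.**

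| q (assumed) | p = 10% | p = 39.2% | Participants added, of 150 |
|---|---|---|---|
| 0% | 0 | 0 | 0 |
| 1% | 0.01 × 0.900 = 0.90 points | 0.01 × 0.608 = 0.61 points | 0.91 to 1.35 |
| 2% | 0.02 × 0.900 = 1.80 points | 0.02 × 0.608 = 1.22 points | 1.82 to 2.70 |
| 5% | 0.05 × 0.900 = 4.50 points | 0.05 × 0.608 = 3.04 points | 4.56 to 6.75 |

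For scale, the Clopper-Pearson 95% half-width at n = 150 is 5.1 points for an observed 10%, 6.7 for 20% and 7.6 for 30%. The addition is smaller than the sampling uncertainty in every row, but it is an overcount in one direction and not random error.

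**The case against.** **Effects on doses other than dose 1.** A reader might infer that only the dose 1 percentages are wrong and that Intervals 2, 3, 6 and 7 are untouched. The documents do not support that. Those intervals use the same date rule, and procedures that can turn up an AE precede the injection at Visits 4 and 9 as well. Nor are draw-related AEs confined to dose 1: the draws at Visits 2, 5 and 10 fall on the inclusive stop dates of Intervals 5, 6 and 7.

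**Comparisons.** A reader might also infer that a dose 1 versus saline comparison is biased. No such contrast is planned. All analyses are descriptive (SAP 5.1), and the safety CIs serve to flag events for clinical follow-up (SAP 5.2.1.2). Both groups have identical procedures and vaccine at Visit 1.

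**Size.** The rate is unknown and may be zero. Protocol 2.3.1 requires the supine position around phlebotomy. Any error overcounts AEs, which is the cautious direction, and related events are tabulated separately. If vaccination is postponed to a later day, AEs from the earlier day fall before the Vax 1 date and so outside Intervals 1, 4 and 10. They could enter Interval 5 only if the Visit 1 date means the first attendance, which the SAP leaves undefined.

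**Implementation.** SAP 2 says that programming rules are written separately, and these might use onset time.

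Most of this stands and limits the point. The last argument does not cure the defect: those rules are to be based on the SAP's methods, and for these intervals the SAP states only dates.

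**Conclusion.** The point holds as a minor error in a stated rule. Read as written, Table 5 counts AEs that begin before the injection on a vaccination day as post-vaccination events, in Intervals 1–7, 10 and 11. Any overcount is likely to be largest for dose 1, because only Visit 1 has the consent period and a pre-dose draw.

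The rule can inflate the percentages; the documents do not establish that it will. Under the assumed rates the any-AE percentage rises by between 0 and 4.5 points, and by less than 2 points if no more than 2% of participants have a pre-injection AE. These figures rest on an assumed pre-dose rate, an assumed post-dose AE percentage and independence of the two. No between-group difference is expected at dose 1.

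**What to change.** In SAP 3.5.1.1 and Table 5, add a rule for AEs with onset on a vaccination date:
- compare the recorded onset time with the recorded injection time;
- exclude events with onset before the injection from Intervals 1–7, 10 and 11;
- list the excluded events separately as pre-vaccination events, so that no safety information is lost;
- keep same-day AEs whose onset time is unknown in the interval.

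The cost is a short addition to the SAP and a small programming step on fields already collected. Reported AE percentages may fall slightly.

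The change has limits. Draw-related events that start after the injection, such as later bruising, would remain counted, as would those arising at the Visit 2, 5 and 10 draws that fall within an interval.
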